Study Overview. Heavy drinkers (N=40) who do not regularly use cannabis but are not cannabis naïve will be recruited for this pilot study involving 3 half-day visits to our lab at CSU. Interested individuals will be phone screened, and eligible subjects will be scheduled for their first visit. For both visits, subjects will be asked to arrive in the lab at 11:15am and will be asked to have someone drive them to the lab and pick them up at the end of the day if possible. If this is not possible we will call a Lyft for them and cover the cost. At the first visit, they will complete informed consent and a demographics form and several questionnaires on psychological functioning and substance use. Subjects will then consume their CBD (30 mg or 200 mg) or placebo. Alcohol administration (up to .8g/kg) will occur about 25 min after CBD ingestion, and testing procedures will occur every 30 minutes for the next 4 hours. The timeframe of the visit was selected because maximum plasma concentration of this CBD product occurs in the blood after 45 minutes (Williams et al 2021) Also, peak BrAC occurs for the alcohol dose we are administering (up to .8g/kg) approx. 1 hour after alcohol ingestion. The order of study visits (CBD 30 mg vs. CBD 200 mg vs. placebo) will be counterbalanced across participants, such that participants will be randomly assigned to complete each the three visits in different orders. Also note that the research assistants running the study will also be blinded to participant condition (and a non-blinded graduate student will prepare the CBD product for the subjects before the session). The three study visits will occur 1 week apart. There will also be 3 venous blood draws for Blood Cannabinoids at both visits. Blood draws will occur before CBD/placebo ingestion (to verify no CBD use prior to experiment), before alcohol consumption and 60 min post-alcohol ingestion. Blood will be assayed for CBD, THC and THC metabolites using High Performance Liquid Chromatography-Mass Spectrometry.

This procedure is:

Other Procedure

Please explain:

Overview of procedures/activities.

Procedure Description

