Laboratory Sessions (CBD 30 mg Session, CBD 200 mg Session and Placebo-CBD Session). At each subject's first session, they will arrive at the lab at approximately 11:15am, undergo informed consent procedures with a trained research assistant, undergo urine pregnancy and drug screening and receive a breathalyzer test. We will use the Intoximeter Alcosensor IV Breathalyzer, which is the gold standard for alcohol research studies. Urine drug screening will test for the presence of illicit drugs (besides cannabis). If urine drug or pregnancy tests are positive, participants will be disqualified from participation. If BrAC is above 0.000, participants will be rescheduled. If all tests are negative, participants will complete a brief demographics form and psychological functioning/substance use questionnaires. Next, they do the first blood draw and will then be given either 30 or 200mg CBD dissolved in water or plain water (as the placebo CBD condition). They will then be asked to wait for 25 minutes in our lab. They will be provided with internet access during this time. Participants are allowed to consume water ad libitum throughout the entire day of the study. Immediately before the alcohol administration procedures begin, subjects will again have their blood drawn and will complete measures of balance/motor performance, inhibitory control, alcohol craving, stimulation and sedation. Specifically, the following measures will be administered to measure alcohol craving, stimulation and sedation: The Biphasic Alcohol Effects Scale (BAES) is a self-report rating scale measuring stimulant and sedative effects of alcohol. It has shown good reliability and validity in AUD. The Subjective High Assessment Scale (SHAS) is a standard self-report measure used to assess subjective responses to alcohol. The Alcohol Urge Questionnaire (AUQ) is a well-established measure of alcohol craving and desire to drink that is commonly used in the context of acute alcohol administration. To test balance/motor function we will use a psychomotor battery designed to capture measures of cognitive and motor impairment in divided attention, decision making, reaction time, motor tracking and balance movements following the intake of drugs or alcohol and designed to be administered repeatedly in a single session to assess changes in impairment without being susceptible to practice effects. Finally, to test inhibitory control we will use the The Flanker Inhibitory Control and Attention Task, which requires participants to focus on a stimulus while inhibiting attention to stimuli flanking it. These measures will be administered on an ipad. Next, participants will consume up to .8g/kg of vodka mixed with orange juice, following procedures from previous alcohol and cannabis co-administration studies. The dose will be reduced 8% for females to adjust for expected BrAC differences between males and females. An .8g/kg dose should produce a peak BrAC of no more than .089% approximately 1 hour after alcohol consumption, which should not significantly exceed the BrAC reached by heavy drinkers during a typical heavy drinking period. There will be a third blood draw at this time (approximately 1 hour after the start of the alcohol administration procedure). As in the three prior human studies of alcohol and CBD co-administration, participants will be asked to consume their alcohol within a 20-min. time period. The above procedures (breathalyzer measurement of BrAC, measures of inhibitory control and balance/motor performance, alcohol craving, stimulation and sedation) will be repeated every 30 min. for 4 hours post-alcohol administration. Participants will be required to reach a BrAC of <.03 before going home, which is estimated to take no more than 4 hours post-alcohol administration, given the elimination rate of alcohol from the body. They will also be required to either have someone pick them up from the lab after the study session is over, or if this is not possible our lab will call them a Lyft, and will cover the cost for them. Participants will be offered snacks after testing is complete to facilitate BrAC reduction. The visit will end at approx. 4:00pm. They will also be required to either have someone pick them up from the lab after the study session is over, or if this is not possible our lab will call them a Lyft. CBD Product. Consistent with the Colorado Department of Agriculture (CDA) and CSU regulations, the 30 mg and 200 mg CBD products will be sourced by Caliper Foods (<https://www.caliperfoods.life/>), which is a CDA compliant product containing <.3%THC (thus qualifying as hemp rather than cannabis, which means it is allowed on CSU's campus). Subjects will consume Caliper's 5% CBD concentrate liquid in water on the day of their CBD study appointment, and they will consume plain water with no CBD on the day of their placebo-CBD appointment. Caliper's CBD readily solubilizes into water within seconds and does not impact flavor, consistency, texture or appearance of the water. Thus, participants will not be able to tell whether they are consuming water containing CBD or plain water. Note that individuals who report very high levels of alcohol consumption on the questionnaires, those that report symptoms of severe depression or suicidality, or those that determine that they do need to seek alcohol treatment will be referred to the Psychological Services Center in the CSU Psychology Department (<https://psychology.colostate.edu/psc/>), Aspenridge recovery (<https://www.aspenridgefortcollins.com/>) and

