
Mountain Crest, which provides inpatient MH services (<https://www.uchealth.org/locations/uchealth-mountain-crest-behavioral-health-center/>). More specifically, if suicidality is revealed during the study session (i.e., if the participant selects a 2 ("I would like to kill myself") or a 3 ("I would kill myself if I have the chance") on BDI item #9), the study procedures will be stopped and the research assistant will call the PI, [name], who has a PhD in Clinical Psychology. [name] will then conduct a risk assessment over the phone. If participants indicate that they have plans, means and intent to harm themselves, and [name] determines that the participant would be a danger to themselves if allowed to leave the session, procedures for hospitalization will be initiated. At this time, [name] (a licensed clinical psychologist in the psychology department) will be called to assist, as a licensed psychologist is needed to sign off on hospitalization procedures. Please note that this is extremely unlikely to happen, given that we will screen individuals out of participating in the study if the report suicidal ideation on the phone screen. However, because we are administering a self-report measure that asks about suicidality, the procedures described above are in place to ensure participant safety.

This procedure is:

Research Activity Involving Participants, Participants Data, or Biospecimens

This procedure is:

Experimental

Where and when will this procedure take place?

Please identify the location of procedures.

Who will conduct this procedure?**Personnel**

[name]

Personnel

[name]

Personnel

[name]

Personnel

[name]

Personnel

[name]

Indicate the frequency and duration of visits/sessions as well as the subject's total time commitment for the study.

Visits will take about 4.5 hours.

Describe how the data will be collected (i.e. in person or online).

In person

Privacy and Confidentiality

Explain how the established data management plan along with consent processes and other elements of the research design address the

following.

Privacy is considered from the perspective of the participant and is a right to be protected. Privacy refers to an individual's interest in controlling others' access to themselves. Based on their privacy interests, participants may want to control:

- The time and place where they give information
- The nature of the information they give

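### No stated step has staff read BDI item 9 before CBD or placebo, and a non-zero answer below 2 carries no stated hold on dosing

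*Combined protocol and SAP*

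**What the plan says.** All of this is in the protocol part of the combined document.

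- **Phone screen.** Procedures, Laboratory Sessions, explains why an in-session crisis is improbable: "given that we will screen individuals out of participating in the study if the report suicidal ideation on the phone screen". No severity is attached.
- **Exclusion list.** The exclusion criteria under Participant Population name suicidal ideation only in connection with a psychiatric diagnosis.
- **In-session rule.** The response applies "if suicidality is revealed during the study session (i.e., if the participant selects a 2" or a 3 "on BDI item #9), the study procedures will be stopped". The research assistant then calls the principal investigator, who assesses risk by telephone.
- **Order of visit-1 steps.** The Study Overview places "several questionnaires on psychological functioning and substance use" at the first visit. Laboratory Sessions puts the urine and breath tests first: "If all tests are negative, participants will complete a brief demographics form". The sentence goes on to the "psychological functioning/substance use questionnaires. Next, they do the first blood draw and will then be given either 30 or 200mg CBD", or plain water as placebo. A 25-minute wait and then alcohol follow.
- **Referral.** Participants to be referred to services include "those that report symptoms of severe depression or suicidality".
- **Other safeguards.** Risks and Benefits provides a clinical psychologist on call at all appointments, an experimenter always present during laboratory procedures, supervision until BAC is below .03, and the chance to discuss discomfort about questions with a clinician.

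**The concern.** The phone screen and the laboratory visit appear to treat the same disclosure differently. Read as written, the phone rule keeps out a person who reports any suicidal ideation. If that person first discloses lower-level ideation on the questionnaire at visit 1, the stated consequence is at most a referral. The only stated conditions for going ahead are the urine and breath tests, which come before the questionnaires.

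This matters because the questionnaire is the natural backstop for anything the phone screen misses, and the protocol itself lists sadness or depression among the possible effects of the alcohol dose. That dose is up to .8 g/kg at each of three visits. If the BDI is completed before dosing, it is the last stated point at which a missed or new disclosure could be caught before the participant takes CBD and alcohol.

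**Working it through.** The plan gives no figure to reproduce, and the point does not depend on alpha, power or sample size. The check is a comparison of the text.

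**1. Thresholds**

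| Where ideation is disclosed | Stated trigger | Stated consequence |
|---|---|---|
| Phone screen (Laboratory Sessions) | Suicidal ideation, no severity given | Screened out |
| Exclusion criteria | Ideation together with a diagnosis | Ineligible |
| In session, item 9 answered 2 or 3 | Met | Procedures stop, investigator called, risk assessed |
| In session, item 9 non-zero but below 2 | Not met | Possible referral; no stop, assessment or hold stated |

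The last row is the gap. Whether it conflicts with the phone rule depends on which of the first two rows the phone script applies. The script is an attachment that is not reproduced.

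**2. Sequence at visit 1**

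Tests, questionnaires, first blood draw, CBD or placebo, 25-minute wait, alcohol. No reading of item 9 is placed between the questionnaires and CBD. Data Management says self-report data are entered on laptops and describes no alert to staff. The stop rule can work only if someone reads the item during the session, so a reading is implied; its timing relative to dosing is not stated.

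**3. Do the other safeguards hold dosing?**

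- Referral sends a person to services; it does not delay the dose.
- The on-call psychologist is there for negative psychological effects and is not linked to an item-9 answer.
- The offer of a clinician is tied to discomfort with the questions.
- Supervision and the BAC discharge limit operate after the alcohol has been given.

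None is a stated hold.

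**4. Effect of an added check on the analysis**

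The check would come before CBD, so the 25-minute interval from CBD to alcohol is unchanged. The SAP times T2 (90 minutes) and T8 (4.5 hours) from the start of the alcohol administration session, so T2 to T8 do not move.

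**5. Staff time**

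Minutes = minutes per reading × participants × visits with the BDI. Two minutes per reading is my assumption. The protocol gives both 20 participants (Participant Population) and 40 (Study Overview).

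- Visit 1 only: 2 × 20 × 1 = 40 to 2 × 40 × 1 = 80 minutes for the whole study.
- All three visits: 2 × 20 × 3 = 120 to 2 × 40 × 3 = 240 minutes.

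**The case against.** The strongest case against has five parts.

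- **The phone rule is a passing reassurance, not an eligibility criterion.** The exclusion list ties ideation to a diagnosis. If the phone script follows that list, lower-level ideation alone would not exclude by phone. This stands: the mismatch between phone and laboratory is not established, and the two passages on eligibility need to be reconciled in any case.
- **A pre-dose reading is probably intended.** The stop rule presupposes that item 9 is read in session, and the questionnaires come before dosing. This also stands. A reader might infer that nobody looks at the answers; the documents do not support that. What remains is unstated timing and the absence of a hold below 2.
- **Different thresholds can serve different purposes.** One rule governs entry and the other an emergency stop that may lead to hospitalization. That is fair, and the difference is not an error in itself. It still leaves no intermediate step for an answer between zero and the emergency level.
- **The step may already exist.** The Data Safety and Monitoring Plan, laboratory safety plan, session-1 questionnaires and phone script are listed as attachments but not shown. The finding is therefore limited to the text available.
- **The risk is contained.** The protocol expects intoxication no greater than participants' usual level, and they are supervised throughout. This lowers the stakes, but it does not replace a check before dosing.

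A reader might also infer that the plan directs alcohol to a person identified as suicidal. It does not: a 2 or 3 stops the session.

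**Conclusion.** The point holds as a minor participant-safety improvement. In the text shown, no step places the reading of item 9 before CBD or placebo, and a non-zero answer below 2 has no stated hold on dosing. Followed to the letter, the plan could dose someone whom its own phone-screen sentence would have kept out.

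Three assumptions carry this: the BDI is among the visit-1 questionnaires given before dosing; a non-zero answer below 2 can express ideation (only the wording of options 2 and 3 is printed); and the attachments not shown do not already contain the step.

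The number of people affected cannot be estimated, because the documents give no rate of lower-level ideation among people who pass the phone screen. No estimand, model or assessment time changes.

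**What to change.** In Procedures, Laboratory Sessions:

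1. After the questionnaires, and before the first blood draw and CBD or placebo, have staff read item 9 at every visit where the BDI is given.
2. Hold dosing for any non-zero answer until the on-call investigator has assessed risk and confirmed eligibility. This is a hold for judgement, not an automatic exclusion.
3. Keep the existing stop for a 2 or 3.

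In the exclusion criteria, align the wording with the phone rule by listing current suicidal ideation regardless of diagnosis, so that staff have a written basis for ineligibility after the phone screen.

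If the safety plans not shown already contain the step, a cross-reference beside the stop rule is enough, together with the alignment of the exclusion wording.

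**Cost.** Short amendment wording, a few staff-minutes per visit to read one item already collected, and an occasional delayed session or rare screen failure. A held session that goes ahead ends later by the length of the call. I give no clock time, because the stated finish is not a safe baseline: the protocol says "The visit will end at approx. 4:00pm", but arrival at 11:15am plus the 25-minute wait plus T8 at 4.5 hours is already 4:10pm, before consent, tests, questionnaires or blood draws.

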Cover Page

Protocol document version date Sept 27, 2021

Document submitted Nov 25, 2023

NCT # NCT06105138

Title: Cannabidiol Effects on Blood Alcohol Level and Intoxication

Statistical Analysis Plan

Prior to hypothesis testing, we will conduct data wrangling and visualizations on the raw data for all outcomes using the R programming language and packages included in tidyverse (Team 2013; Wickham et al. 2019) (e.g., ggplot2 (Wickham 2016)). To examine changes over time in BrAC, alcohol craving, affect, sedation, and stimulation during the descending limb of the BrAC curve (T2 – T8, see Figure 1) and to compare these changes by sex and condition, we will run a series of Multilevel Structural Equation Models (MSEM; (Mehta and Neale 2005) using Mplus 8 (Muthén and Muthén 2017). Due to the research design, where each participant completed each condition (placebo, 30mg CBD and 200mg CBD) and within each condition there were 7 repeated measures of interest, MSEM need to be run with a latent growth curve on the within-level to capture the change over time. Repeated measures of interest were taken at timepoints T2-T8, which represent the descending limb of the BrAC curve. We will focus on the descending limb because evidence suggests that some subjective effects of alcohol may be particularly prominent during the descending limb (Pihl et al. 2003; Brick 2006). In addition, prior medication studies have demonstrated that notable medication effects such as reduction in craving and stimulation are observed in both the descending and ascending limb (Ray and Hutchison 2007), but some unique effects such as increased tension may be specific to the descending limb (Ray et al. 2008). Another advantage of focusing on the descending limb is that changes during this time are expected to be approximately linear (e.g., BrAC decreases linearly (Posey and Mozayani 2007)), which supports a more straightforward interpretation of model results. Note that T2= 90 minutes after the start of the alcohol administration session and T8=4.5 hours after the start of the alcohol administration session.

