Risk of Phlebotomy. When having blood drawn, participants may experience some discomfort as a result of the needle prick in the arm. Some bruising or slight bleeding may occur. Although infection is possible, it is extremely rare, because the needle is sterile and disposable. Occasionally, people feel lightheaded or faint when blood is drawn, but the volume taken will be small (no more than 10mL is drawn for each of three blood draws). Protection Against Risks of Phlebotomy. Individuals trained in phlebotomy will conduct all blood draws. They have completed IBC training, BBP, BSL1, BSL2 and Hazardous Waste trainings and have demonstrated competence in phlebotomy, following the [name] lab's SOP. Individuals who may draw blood during the study are: [name], [name], [name], [name] and [name]. Risks of Alcohol Administration. Adverse effects of alcohol such as intoxication, acute mood shifts (e.g., feelings of sadness or depression), and odd perceptual experiences are possible. However, individuals are recruited because they are heavy drinkers, defined as consuming >5 drinks [>4 for women] per occasion) at least 5 days/month in the past 3 months. The dose of alcohol given in the study is only designed to bring BAC to a maximum of .089, which is not higher than a typical BAC reached by individuals drinking 4-5 drinks in a single occasion. Thus, individuals in the present study are not likely to experience alcohol intoxication beyond the level that they normally experience in their daily life as a heavy drinker. Protection Against Risks of Alcohol Administration. Several steps will be taken to minimize risk to participants as a result of the acute effects of alcohol including those based on guidelines provided by NIAAA (NIAAA Recommended Council Guidelines on Ethyl Alcohol Administration in Human Experimentation; NIAAA, 2005). More specifically, the following protections are in place: First, participants will be excluded from the study if they have a medical condition, have an alcohol use disorder (AUD) or another substance use disorder (SUD), are current in treatment for or seeking treatment for AUD or another SUD, or have a medical condition that may contraindicate the consumption of alcohol. Urinalysis drug screens will be used at both laboratory sessions to exclude for any illicit drug use. Participants will only be included in the study if they are current heavy drinkers who report 5 binge drinking episodes per month over the last three months (note that a binge is defined by SAMHSA as consuming 5 drinks per occasion [4 for women]). Study staff will closely monitor participant BAC via breathalyzer throughout the alcohol administration protocols to ensure that BAC never exceeds .089 (which is roughly the equivalent of four standard drinks and is at the legal limit for alcohol impairment) following established alcohol-administration procedures. Thus, the amount of alcohol provided over the sessions will not exceed the dosage level consistent with participants' normal drinking practices. At both laboratory visits, a picture ID will be required to prove age eligibility (> 21 years). Female participants will be required to take a private urine sample pregnancy test on the day of both laboratory sessions. In case of any positive reading, participants will not be eligible to participate. The results of all pregnancy tests will be kept confidential and the tests will be safely discarded. During the laboratory procedures, an experimenter will be present at all times. Participants will be required to remain in the laboratory until their BAC <.03 g/dL. Participants will be supervised by the experimenter during this period. Participants will also have an opportunity to ask questions of the experimenter. In addition, [name] (a trained clinical psychologist) will be on call during all study appointments if any participant experiences negative psychological effects. Risks of CBD Administration. There may be mild physical side effects of CBD consumption, including nausea, fatigue and irritability. In addition, CBD can increase the level in your blood of the blood thinner coumadin. Individuals will be screened out and not allowed to participate in this study if they are taking this medication.

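### Internal inconsistency in a safety protection: alcohol is given at three sessions, but the pregnancy test, urine drug screen, picture ID and cannabinoid blood draws are written for two

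*Combined protocol and SAP*

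**What the plan says.** **Three sessions.** The SAP describes a within-person design "where each participant completed each condition (placebo, 30mg CBD and 200mg CBD"). The Study Overview under Procedures says "The three study visits will occur 1 week apart", and the Laboratory Sessions heading names a 30 mg, a 200 mg and a placebo session. The aims compare CBD plus alcohol with placebo plus alcohol, so alcohol is part of every session.

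**Checks at two.** Under Risks and Benefits, the paragraph on protection against the risks of alcohol administration says "Female participants will be required to take a private urine sample pregnancy test on the day of both laboratory sessions" and "Urinalysis drug screens will be used at both laboratory sessions to exclude for any illicit drug use". It also asks for picture ID at both visits. On the consequence it says "In case of any positive reading, participants will not be eligible to participate".

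**Draws at two.** The Study Overview says "There will also be 3 venous blood draws for Blood Cannabinoids at both visits", and then: "Blood draws will occur before CBD/placebo ingestion (to verify no CBD use prior to experiment), before alcohol consumption and 60 min post-alcohol ingestion". It also sets the arrival time for both visits.

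**Checks at the first.** The Laboratory Sessions text introduces the urine tests and breathalyzer in its account of each participant's first session, next to consent and the demographics form. It later refers to one CBD appointment and one placebo appointment.

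**The concern.** Pregnancy and a failed urine drug screen are exclusion criteria, and the Laboratory Sessions text disqualifies a participant on a positive result. The protocol rates the study as greater than minimal risk and lists same-day testing among its protections. Such a protection should cover every dosing day in its own words. Because the protocol plans testing on session days, and not once at entry, it does not itself treat one negative result as good for later visits.

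The pre-dose blood draw is the protocol's own check on earlier CBD use. Visit order is counterbalanced, so placebo can fall at any of the three visits and the check is useful at each. Its role is limited: the text available ties no rescheduling or disqualification rule to the result.

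**Working it through.** The plan gives no figure to reproduce here. The check is a count of sessions followed by a comparison of texts.

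**Number of sessions**

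- Conditions (SAP): placebo + 30 mg + 200 mg = 3.
- Visits (Study Overview): 3, one week apart.
- Payment (Participant Compensation/Costs): maximum / per session = 297 / 99 = 3.

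All three sources agree on three.

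**What each text requires, read literally**

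| Item | Where stated | Sessions named |
|---|---|---|
| Pregnancy test | Risks and Benefits | 2 |
| Urine drug screen | Risks and Benefits | 2 |
| Picture ID | Risks and Benefits | 2 |
| Arrival time | Study Overview | 2 |
| Cannabinoid draws | Study Overview | 2 |
| Urine tests and breathalyzer | Laboratory Sessions | first session only |

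**Size of the gap**

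- Sessions planned minus sessions named: 3 − 2 = 1.
- Blood draws: 3 per session × 3 sessions = 9 planned; 3 × 2 = 6 specified.

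**Does another part of the text close the gap?** The Laboratory Sessions text is the only detailed account of a session, so it is the natural place to look. It does not say which of its steps recur. Its half-hourly repetition concerns the measures taken after alcohol within one session, not the pre-dose checks. Literally, one section gives one session and the other gives two. No available text gives three.

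**Why leftover wording is the likely cause.** The word *both* recurs in two separate sections and is applied to matters as different as arrival time and pregnancy testing. The contrast between a single CBD appointment and a single placebo appointment fits a two-visit design with one CBD dose. This is an inference; the text does not state it.

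**The case against.** The strongest reply is that the Laboratory Sessions text already shows the intent. Its heading covers all three sessions, and one walkthrough runs from the urine tests and first blood draw through CBD or placebo to alcohol and testing. If the mention of the first session confined the urine tests to that day, the same reading would leave dosing undescribed on the other two. The risk paragraph also speaks of any positive reading and of all pregnancy tests, which fits repeated testing. Nor does the text say which session would go without, so staff could not carry out a two-of-three schedule from it.

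Most of this stands. It makes repetition the likely intent and makes the problem an internal inconsistency, not a design choice. It does not correct the word *both* in an operative safety rule.

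A second reply is that the schedule may be set out elsewhere. The consent form, the data safety monitoring plan and the lab safety plan are listed as attachments but were not available, nor were some other parts of the file. This version is also marked as superseded. That stands too: the finding concerns the wording of the available text, not the whole of the study's paperwork.

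A reader might infer that the sponsor chose to leave one dosing day unchecked, or that women were given alcohol untested. The documents support neither reading, since they contain no such decision and say nothing about conduct.

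**Conclusion.** The inconsistency is real and should be corrected. Three dosing sessions are planned, and the stated pregnancy test, urine drug screen, picture ID check and cannabinoid draws cover two. Confidence is high on the mismatch and moderate on its cause. The conclusion assumes that alcohol is given at all three sessions, which the aims and the session description both indicate, and that no unavailable document already sets the schedule.

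A reader might also infer that the analysis is affected. It is not on this evidence: the point touches no sample size, power or model specification.

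**What to change.** - **Risks and Benefits, protection against risks of alcohol administration:** change *both* to *all three* for the urine drug screen, the picture ID and the pregnancy test.
- **Study Overview:** make the same change for the arrival time and the blood draws.
- **Laboratory Sessions:** state that the pregnancy test, urine drug screen, breath alcohol check and pre-dose blood draw are done before dosing at every session, and that consent and demographics are done once. Replace the single CBD appointment with the two CBD appointments.

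If *both* already meant every session, practice does not change. Otherwise the cost is at most one more urine test set and three more draws per participant. A few participants may be excluded or rescheduled at a later session, which would lose or delay some within-person data.
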